10.3 Methods for Evaluation of Measurable Disease

All measurements should be taken and recorded in metric notation, using a ruler, calipers, or digital measurement tool. All baseline evaluations should be performed as closely as possible to the beginning of treatment and never more than 14 days before the beginning of the treatment. The same method of assessment and the same technique should be used to characterize each identified and reported lesion at baseline and during follow-up

10.4 Evaluation of Best Response

The best overall response is the best response recorded from the start of the treatment until disease progression (taking as reference for progressive disease the smallest measurements recorded since the treatment started). If a response recorded at one scheduled MRI does not persist at the next regular scheduled MRI, the response will still be recorded based on the prior scan, but will be designated as a non-sustained response. If the response is sustained, i.e. still present on the subsequent MRI at least four weeks later, it will be recorded as a sustained response, lasting until the time of tumor progression. Participants without measurable disease may only achieve SD or PD as their best “response.”

10.5 Modified RANO (iRANO)¹¹¹: Study Continuation Beyond Initial Progressive Disease

Immunotherapeutic agents such as pembrolizumab may produce antitumor effects by potentiating endogenous cancer-specific immune responses which may manifest as initial worsening of enhancement and edema on MRI or CT scans (i.e. pseudoprogression). In addition, the response patterns seen with immunotherapeutics may extend beyond the typical time course of responses seen with cytotoxic agents, and can manifest a clinical response after an initial increase in tumor burden or even the appearance of new lesions. For these reasons, the immune-related response criteria (irRC) have endorsed continuation of study therapy beyond initial radiographic evidence of progression for clinically stable patients undergoing immune based therapies.¹⁰⁵

A major advance of the RANO criteria¹⁰⁴ to assess response in neuro-oncology over the previously used Macdonald criteria¹⁰⁶ includes recognition of the prevalence of pseudoprogression during the first three months following completion of radiation and daily temozolomide.^{107,108} Specifically, RANO permits patients with such progressive MRI findings to continue temozolomide therapy for up to three months in order to avoid inaccurately classifying such patients as progressive. Furthermore, RANO permits patients with progressive radiographic findings at anytime to continue current therapy pending follow-up imaging if the etiology of progressive imaging findings is unclear. Standard RANO may not provide an accurate response assessment of immunotherapeutic agents such as pembrolizumab.

Therefore, the following adaptations of the RANO criteria will be used to assess response for patients treated on this study in an exploratory fashion (Table 8):

- Potential Pseudoprogression: If radiologic imaging shows initial PD, subjects who are not experiencing significant clinical decline (e.g. significant decrease in KPS see section 10.2.3), may be allowed to continue study treatment for up to three months. Patients should

be closely monitored with MRIs every cycle (approximately every 6 weeks) during this period. Patients who have radiographic evidence of further progression after up to three months, or who decline significantly at anytime, will be classified as progressive with the date of disease progression back-dated to the first date that the subject met criteria for progression and such subjects will be discontinued from study therapy. Although the kinetics of pseudoprogression due to immune checkpoint blockade among glioblastoma patients is currently unknown, three months is a reasonable estimate based on: 1) the peak time for XRT/daily temozolomide-related pseudoprogression is usually within three months of completion for glioblastoma patients^{107,108} and; 2) three months is also the most common timeframe for pseudoprogression observed among patients with advanced melanoma or other solid tumors treated with PD-1/PD-L1 immune checkpoint blockade to date.^{66,69,109}

Among patients on this study with initial radiographic PD, tumor assessment should be repeated regularly (every cycle, approximately every 6 weeks) in order to confirm PD with the option of continuing treatment as described below while awaiting radiologic confirmation of progression. If repeat imaging shows a stabilization or reduction in the tumor burden compared to the initial scan demonstrating PD, treatment may be continued / resumed. If repeat imaging after up to three months confirms progressive disease, then the date of disease progression will be the first date the subject met criteria for progression and subjects will be discontinued from study therapy. Subjects who have confirmed disease progression will discontinue study medication and enter the follow up/survival phase of the study. In determining whether or not the tumor burden has increased or decreased, investigators should consider all target lesions as well as non-target lesions.

- Tumor Enhancement to Define Progression: RANO expanded the previously utilized Macdonald criteria¹⁰⁶ to include the development of “significantly” increased T2 or FLAIR abnormality in the definition of progressive disease because such changes can be a major component defining radiographic progression following therapeutic use of VEGF/VEGFR-targeting therapeutics which are known to elicit potent anti-permeability changes that limit contrast uptake. However, immune based therapies are expected to be associated with inflammatory changes that may include edema. Therefore, radiographic progressive disease will be defined by assessment of enhancing tumor and will not declare tumor progression based on the presence of T2 or FLAIR changes alone as outlined in RANO because:
 - There is no expectation that immunotherapy agents including PD-1 inhibitors will falsely diminish enhancing tumor burden as has been noted with anti-angiogenic therapies; and
 - Immune based therapies are expected to induce inflammatory responses which may be associated with increased edema and T2/FLAIR changes. Such radiographic finding may inaccurately be interpreted to represent tumor progression (i.e. pseudoprogression).

In subjects who have initial evidence of radiographic PD, it is at the discretion of the treating physician whether to continue a subject on study treatment for up to three months pending

confirmation of PD on follow-up imaging. This clinical judgment decision should be based on the subject's overall clinical condition, including performance status, clinical symptoms, and laboratory data. Subjects may receive study treatment while waiting for confirmation of PD if they are not experiencing significant clinical decline and the subject is adequately tolerating study therapy (if a subject is required to discontinue study treatment for toxicity as defined per protocol section 5, then they must be taken off-treatment).

When feasible, study therapy should not be discontinued until radiographic progression is confirmed. This allowance to continue treatment despite initial radiologic progression takes into account the observation that some subjects can have a transient tumor flare in the first few months after the start of immunotherapy, but with subsequent disease response.¹⁰⁵ Subjects that are exhibiting significant neurologic decline are not required to have repeat imaging for confirmation of progressive disease.

Table 8 Imaging and Treatment After 1st Radiologic Evidence of PD

	No Significant Neurologic Decline		Significant Neurologic Decline	
	Imaging	Treatment	Imaging	Treatment
1 st radiologic evidence of PD	Repeat imaging (every cycle, approximately every 6 weeks) for up to 3 months to confirm PD	May continue study treatment at the Investigator's discretion for up to 3 months while awaiting confirmatory scans	Repeat imaging >6 weeks later to confirm PD if possible	Discontinue treatment
Repeat scan up to 3 months after 1 st radiologic evidence confirms PD	No additional imaging required; date of tumor progression back-dated to date of initial radiographic PD	Discontinue treatment	No additional imaging required	Not applicable
Repeat scan shows SD, PR or CR	Continue regularly scheduled imaging assessments every 6 weeks	Continue study treatment at the Investigator's discretion	Continue regularly scheduled imaging assessments every 6 weeks	May restart study treatment if condition has improved and/or clinically stable per Investigator's discretion

Participants with progressive radiographic findings are encouraged to undergo surgical intervention in order to delineate pseudoprogression due to inflammation associated with PD-1 blockade from true tumor progression. Participants with histopathologic findings of significant immune infiltrate and evolving gliosis will be allowed to continue study therapy. In contrast, those with clear evidence of progressive tumor by histopathologic evaluation will be defined as progressive and discontinued from study therapy. For such patients, the date of tumor progression will be the first date the participant met radiographic criteria for PD

10.6 Central Radiology Review

The central review of neuroimaging (MRI or CT) will be performed at Dana-Farber Cancer Institute or UCLA (as determined by Overall PI) on participants when requested from the DFCI Coordinating Center on behalf of the Overall PI. All films of all views from pre-registration (including pre-enrollment scans documenting progression prior to study interventions) and subsequent scans (including all on-study and follow-up scans) will be requested for central review. CDs are preferred.

A copy of all scan reports should be attached for inclusion in the submission. Once the Central Review is complete the Reviewing Physician will document the review results. Once the Central Review is complete, the central review results may be made available to the local PI or treating investigator.

When requested from the DFCI Coordinating Center, please send a copy of all scans to:

[name] c/o [name]
Center for Neuro-Oncology
Dana-Farber Cancer Institute
[name]
Boston, MA 02215
ph: [contact]
[contact]
[contact]

A memo must be submitted to the DFCI Coordinating Center each time submissions are made including DFCI study number, participant identifiers and details of what is being submitted.

The submitting institution is responsible for the costs of shipping and handling.

11. DATA REPORTING / REGULATORY REQUIREMENTS

Adverse event lists, guidelines, and instructions for AE reporting can be found in Section 7.0 (Adverse Events: List and Reporting Requirements).

11.1 Data Reporting

11.1.1 Method

The Office of Data Quality (ODQ) will collect, manage, and perform quality checks on the data for this study.

11.2 Responsibility for Data Submission

All investigative sites are responsible for submitting data and/or data forms to the Office of Data Quality (ODQ) in accordance with DF/HCC policies.

Form	Submission Timeline
Eligibility Checklist	Complete prior to registration with ODQ
On Study Form	Within 30 days of registration
Baseline Assessment Form	Within 30 days of registration
Treatment Form	Within 14 days of treatment administration
Adverse Event Report Form	Within 14 days of AE assessment/notification
Response Assessment Form	Within 14 days of the response assessment
Off Treatment/Off Study Form	Within 14 days of completing treatment or being taken off study for any reason
Follow up/Survival Form	Within 14 days of the protocol defined follow up visit date or call

11.3 Data Safety Monitoring

The DF/HCC Data and Safety Monitoring Committee (DSMC) will review and monitor toxicity and accrual data from this study. The committee is composed of medical oncologists, research nurses, pharmacists and biostatisticians with direct experience in cancer clinical research. Information that raises any questions about participant safety will be addressed with the Overall PI and study team.

The DSMC will review each protocol up to four times a year with the frequency determined by the outcome of previous reviews.. Information to be provided to the committee may include: up-to-date participant accrual; current dose level information; DLT information; all grade 2 or higher unexpected adverse events that have been reported; summary of all deaths occurring with 30 days

of intervention for Phase I or II protocols; for gene therapy protocols, summary of all deaths while being treated and during active follow-up; any response information; audit results, and a summary provided by the study team. Other information (e.g. scans, laboratory values) will be provided upon request.

11.4 Multicenter Guidelines

This protocol will adhere to the policies and requirements of the DF/HCC Multi-Center Data and Safety Monitoring Plan (Appendix B). The specific responsibilities of the Overall PI, Coordinating Center, and Participating Institutions and the procedures for auditing are presented in Appendix B.

- The Overall PI/Coordinating Center is responsible for distributing all IND Action Letters or Safety Reports to all participating institutions for submission to their individual IRBs for action as required.
- Mechanisms will be in place to ensure quality assurance, protocol compliance, and adverse event reporting at each site.
- Except in very unusual circumstances, each participating institution will order the study agent(s) directly from supplier. A participating site may order the agent(s) only after the initial IRB approval for the site has been forwarded to the Coordinating Center.

12. STATISTICAL ANALYSIS PLAN

This section outlines the statistical analysis strategy and procedures for the study. If, after the study has begun, changes are made to primary and/or key secondary hypotheses, or the statistical methods related to those hypotheses, then the protocol will be amended (consistent with ICH Guideline E-9). Changes to exploratory or other non-confirmatory analyses made after the protocol has been finalized, along with an explanation as to when and why they occurred, will be listed in the Clinical Study Report (CSR) for the study. Post hoc exploratory analyses will be clearly identified in the CSR.

12.1 Statistical Analysis Plan Summary

This section contains a brief summary of the statistical analyses for this trial.

Stage 1:

The primary outcome, tumor infiltrating T lymphocyte (TIL) density, will be assessed by comparing Group A versus Group B.

Stage 2:

The primary outcome, cell cycle and cancer proliferation genetic signature, will be assessed by comparing Group A versus Group B.

Stage 1 and stage 2:

The secondary endpoint, PFS6, will be assessed using pooled Group A and Group B patients and compared to appropriate historical controls.

12.1.1 Efficacy Analyses

The primary and key secondary endpoints, primary analysis population, and statistical methods that will be employed for the efficacy analyses are discussed in detail in the following sections.

12.1.2 Safety Analyses

Adverse events will be graded according to Common Terminology Criteria for Adverse Events (CTCAE) version 5.0. All patients who receive any amount of Pembrolizumab will be evaluable for toxicity. The All-Patients-as-Treated population will be employed for safety analyses.

12.2 Statistical Analysis Plan

12.2.1 Responsibility for Analyses

The statistical analysis of the data obtained from this study will be the responsibility of the study responsible biostatistician.

This trial is being conducted as an open-label study, i.e., subjects, investigators, and SPONSOR personnel will be aware of subject treatment assignments after each subject is enrolled and treatment is assigned.

12.2.2 Hypotheses/Estimation

Objectives and hypotheses of the study are stated in Section 1.0.

12.2.3 Power and Sample Size for primary endpoint

Stage 1:

Group B is an independent concurrent control to evaluate TIL density in Group A due to the infeasibility of multiple resections within a short time period for patients with recurrent GBM. Patients will be randomly assigned to either group A or B with a 1:1 randomization ratio prior to surgery. Based on our preliminary data, the mean of TIL density is estimated to be 0.4 (T cell per nucleating) (SD = 0.5) in the control group (Group B). Fifteen patients per group (total of 30 evaluable) achieve 85% power to detect an increase of 0.5 of TIL density comparing Group A versus Group B at an alpha level of 0.05 (1-sided) using a two-sample t-test.

Stage 2:

An extension based on interim data has the primary scientific endpoint of evaluating the cell cycle signature in patients receiving neoadjuvant pembrolizumab. This extension will aim to enroll 25 additional patients with a goal of 20 evaluable patients to Group A. Group B is an independent

concurrent control to evaluate the cell cycle-related gene signature in Group A. Based on the preliminary data, the mean tumor cell cycle-related gene expression signature is estimated to be -0.3 for neoadjuvant pembrolizumab (SD=0.66) and +0.37 for control (SD=0.64), which corresponds to an effect size of 1.1. With the addition of 20 more patients in Group A, the one-sided two-sample T-test (alpha level: 0.05) will have 81.73% power to detect an effect size of 1.1 for the difference of tumor cell cycle-related gene expression signature between the two groups.

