Trial Blinding	Unblinded, open-label
Treatment Groups	Pembrolizumab presurgery at 200mg followed by Pembrolizumab at 200 mg every 3 weeks post surgery (Group A). No therapy presurgery followed by pembrolizumab at 200 mg every 3 weeks post surgery (Group B)
Number of trial subjects	Approximately 30 evaluable patients will be enrolled in Stage 1 of the trial, an additional 20 evaluable patients will be enrolled in Stage 2 .
Estimated duration of trial	The sponsor estimates that the trial will require an additional 18 months to complete Stage 2 enrollment.
Duration of Participation	Each subject will participate in the trial from the time the subject signs the Informed Consent Form (ICF) through the final protocol-specified contact. In the first stage of the trial (Stage 1), after a screening phase of 14 days, eligible subjects will be randomized into two groups (Group A and Group B). In the second stage of the trial (Stage 2), an additional 25 patients will be screened for a goal of 20 evaluable patients to be assigned to Group A only. Group A will receive one dose of pembrolizumab at 200 mg within 14± 5 days prior to surgery. Group A patients will receive Pembrolizumab at 200 mg every three weeks after surgery. Group B patients will not receive pembrolizumab prior to surgery but will receive pembrolizumab at 200 mg every three weeks after surgery. Post-surgically, both groups (A and B) will receive treatment during each 6-week dosing cycle. Treatment with pembrolizumab therapy will continue until 1) documented confirmed disease progression, unacceptable adverse event(s), intercurrent illness that prevents further administration of treatment, investigator's decision to withdraw the subject, subject withdraws consent, pregnancy of the subject, noncompliance with trial treatment or procedure requirements; or 2) administrative reasons. After the end of treatment, each subject will be followed for 30 days for adverse event monitoring (serious adverse events will be collected for up to 90 days after the end of treatment). Subjects who discontinue for reasons other than disease progression will have post-treatment follow-up for disease status until disease progression, initiating a non-study cancer treatment, withdrawing consent, or becoming lost to follow-up. All subjects will be followed by telephone or medical record review for overall survival until death, withdrawal of consent, or the end of the study.

STUDY SCHEMA

Stage 1

Study Schema

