Our initial hypothesis as reflected in the design of Stage 1 of the trial, is that a functional immune defect exists within the T lymphocyte compartment in recurrent/progressive glioblastoma patients. The neoadjuvant use of pembrolizumab (PD-1 blocking mAb) in this patient population will lead to a statistically significant increase in tumor infiltrating lymphocytes when compared to a concurrent control population. The combination of tumor tissue and optional imaging evaluations should provide insight into immune activation, antitumor effect and toxicity with immune checkpoint inhibitors.

An interim analysis of data from 35 enrolled patients from October 2016 to September 2017 in this trial has also shown that patients who were randomized to receive neoadjuvant pembrolizumab, with continued adjuvant therapy following surgery (Group A), had significantly extended overall survival compared to patients that were randomized to receive adjuvant, post-surgical PD-1 blockade alone (Group B) (hazard ratio = 0.39; P = 0.04, log-rank test). Neoadjuvant PD-1 blockade was associated with upregulation of T cell and interferon- γ -related genes, but

downregulation of cell cycle-related genes within the tumor, which was not seen in patients that received adjuvant therapy alone¹¹². Therefore, in a second stage extension of this trial (Stage 2), the specific effect of neoadjuvant pembrolizumab on the cell cycle and cancer proliferation related genetic signature within the tumor microenvironment of progressive/recurrent glioblastoma patients will be evaluated.

Specific procedures to be performed during the trial, as well as their prescribed times and associated visit windows, are outlined in the Study Calendar - Section 9.

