1.2 Primary Objectives & Hypothesis

Stage 1:

1.2.1 Objective: To test the hypothesis that administration of pembrolizumab (MK-3475) will induce statistically significant increases in tumor infiltrating T lymphocyte (TIL) density in recurrent/progressive GBM patients compared to an untreated concurrent control versus the null hypothesis of no difference the treatment and control groups. (Group A vs. Group B).

Hypothesis: Our hypothesis is that a functional immune defect exists within the T lymphocyte compartment in recurrent/progressive glioblastoma patients. The neoadjuvant use of pembrolizumab (PD-1 blocking mAb) in this patient population will lead to a statistically significant increase in tumor infiltrating lymphocytes when compared to a concurrent control population.

Stage 2:

1.2.2 Objective: To test the hypothesis that administration of pembrolizumab (MK-3475) will lead to statistically significant changes, specifically decreased expression of the cell cycle/cancer proliferation related genetic signatures, within the tumor microenvironment of recurrent/progressive GBM when compared to an untreated concurrent control versus the null hypothesis of no difference the treatment and control groups. (Group A vs. Group B).

Hypothesis: Our hypothesis is that neoadjuvant use of pembrolizumab (MK-3475) will lead to statistically decreased expression in the cell cycle/cancer proliferation related genetic signature as measured by RNA sequencing when compared to a concurrent control population.

For both Stage 1 and Stage 2:

1.2.3 Objective: To evaluate safety of study drug in this patient population.

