5. TREATMENT PLAN

This is a pilot surgical trial to evaluate early immunologic pharmacodynamic parameters for the PD-1 checkpoint inhibitor, pembrolizumab (MK-3475), in patients with surgically accessible recurrent/progressive glioblastoma. The principle goal of this study is to understand, in surgically resectable recurrent/progressive GBM, if neoadjuvant pembrolizumab elicits a systemic immunologic response, a tumoral immunologic response and toxicity and if that response can be correlated with other non-invasive measures of pembrolizumab bioactivity (tumor, blood, imaging, and clinical outcomes). The study includes 2 stages, in the first stage (**Stage 1**), for optimal understanding of the effect of the drug on tumor tissue patients will be randomized in to Group A or Group B. In the second stage (**Stage 2**), additional patients will be enrolled to an expansion arm of Group A only to specifically study the effect of the drug on cell cycle/cancer proliferation related genetic signature.

Stage 1:

Groups A and B: Patients will be randomly assigned to either group A or B with a 1:1 randomization ratio prior to surgery. Patients in all groups will receive the study drug pembrolizumab after tumor resection. Only Group A will receive a single infusion of pembrolizumab of 200mg 14± 5 days prior to surgery (when scheduling, please keep in mind that the two pre-surgical plasma samples should be drawn greater than 10 days apart - see Table 6 for full details). Group B will not receive study drug prior to surgery. **This randomization scheme should not negatively impact study accrual and will provide an invaluable control cohort for PD evaluations.**

Group A: Neoadjuvant/adjuvant evaluation: Fifteen eligible patients will receive a single infusion of pembrolizumab of 200mg 14± 5 days prior to scheduled surgical resection for

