Group B: adjuvant evaluation: Fifteen eligible patients will not receive study drug prior to scheduled surgical resection for recurrent/progressive glioblastoma. The two required pre-surgical plasma samples should be drawn greater than 10 days apart - see Table 6 for full details). Tumor samples will be obtained at time of surgery. The tissue from this surgery (fresh, frozen and FFPE) and the archived tissue from the most recent surgery prior to registration revealing glioblastoma (FFPE) will be processed so as to best achieve the primary, secondary and exploratory PD objectives. After recovery from surgery (once participant has recovered from surgery, but no more than 35 days following surgery), patients will begin Q 3 week pembrolizumab at 200mg IV until tumor progression or adverse event requiring discontinuation of study drug. Blood samples will be obtained as pharmacodynamic markers throughout the study. Dose decreases and symptomatic management will occur based upon preset adverse event determination. DLTs will not be determined. The toxicity evaluation period will begin with registration and extend to 30 days after last treatment day. Patients will be followed for MRI changes, clinical exam and steroid doses from the registration period and extend to the second progression. After second progression, patients will be followed every 3 months for vital status until death.

Stage 2:

Group A expansion only: For this stage of the study, 25 additional patients will be enrolled to Group A only with a goal of 20 evaluable patients.

Expansion of Group A: Neoadjuvant/adjuvant evaluation: An additional 20-25 patients will receive a single infusion of pembrolizumab of 200mg 14± 5 days prior to scheduled surgical resection for recurrent/progressive glioblastoma (when scheduling, please keep in mind that the two pre-surgical plasma samples should be drawn greater than 10 days apart - see Table 6 for full details). Tumor samples will be obtained at time of surgery. The tissue from this surgery (fresh, frozen and FFPE) and the archived tissue from the archived tissue from the most recent surgery prior to registration revealing glioblastoma (FFPE) will be processed so as to best achieve the primary, secondary and exploratory PD objectives. After recovery from surgery (once participant has recovered from surgery, but no more than 35 days following surgery), patients will resume Q 3 week pembrolizumab at 200mg IV until tumor progression or adverse

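### For the 20 new Stage 2 patients, Group B is a Stage 1 control, neither concurrent nor randomised, so the Stage 2 primary test is not an independent 5% confirmation

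*Combined protocol and SAP*

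**What the plan says.** The control is described as concurrent in two places. The Stage 2 objective (section 1.2) tests for lower expression of the cell cycle signature "when compared to an untreated concurrent control versus the null hypothesis", and its hypothesis repeats the idea: "as measured by RNA sequencing when compared to a concurrent control population". Section 12.2.3 calls Group B a "concurrent control to evaluate the cell cycle-related gene signature in Group A" and powers a one-sided two-sample t-test at 0.05.

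The enrolment text says otherwise. In the synopsis, "an additional 25 patients will be screened for a goal of 20 evaluable patients to be assigned to Group A only". In section 5, "additional patients will be enrolled to an expansion arm of Group A only", and again "25 additional patients will be enrolled to Group A only with a goal of 20 evaluable patients". No place adds a Group B patient in Stage 2.

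On timing, section 1.1 refers to "An interim analysis of data from 35 enrolled patients from October 2016 to September 2017 in this trial has also shown" a survival difference. It goes on to report that cell cycle genes were downregulated with neoadjuvant treatment but not in the adjuvant-only group, and gives this as the reason for Stage 2. The synopsis adds: "The sponsor estimates that the trial will require an additional 18 months to complete Stage 2 enrollment". Section 12.2.3 also says that the extension rests on interim data.

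Section 12.2.6.1 plans a Student's t-test of the signature between the two groups. It does not say which Group A patients enter, and it makes no allowance for enrolment period or for reuse of Stage 1 data. The power statement in 12.2.3 speaks of adding 20 patients to Group A, which points to a pooled Group A.

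**The concern.** Two features of the Stage 2 comparison are hidden by the word concurrent.

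First, for the new patients the comparison is with people enrolled in an earlier period under a different allocation scheme. A drug effect cannot be separated from a difference between periods in case mix, surgery, or sample handling and sequencing.

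Second, the Group B data belong to the contrast that suggested the hypothesis. If chance made Group B look high on the signature at the interim, that chance component stays in the final test. If Stage 1 Group A is pooled in, its chance component stays too.

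At stake is how a primary-endpoint result is read. A p-value reported against a concurrent control would carry more weight than this design can give it.

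**Working it through.** **1. The texts side by side.** Sections 1.2 and 12.2.3 say concurrent; the synopsis and section 5 say Group A only. The label is right for Stage 1 Group A, which was randomised 1:1 against Group B. It is wrong for the 20 new patients. With 15 evaluable Stage 1 patients per group (sections 5 and 12.2.3), a pooled Group A has 15 + 20 = 35, so the label fails for 20 of 35.

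**2. The plan's own figure.** Power is taken from the noncentral t with noncentrality d√(n₁n₂/(n₁+n₂)), where d = 1.1 and alpha is one-sided 0.05.
- 35 v 15: 1.1 × √(525/50) = 3.56, df 48, power 96.9%.
- 20 v 15: 1.1 × √(300/35) = 3.22, df 33, power 93.4%.

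Neither gives the stated 81.73%. That is a separate matter, but it bears on the number of controls. A configuration of 20 v 8 gives 82.0%, so the plan may have had fewer than 15 controls with data in mind. The documents do not give the number.

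**3. Effect of reuse (illustration).** Assumptions: no drug effect, normal data with SD 1, Stage 1 of 15 v 15, 20 new A patients, pooled-variance t-test, one-sided 0.05, rejection in favour of A (lower signature). There were 300,000 to 1,000,000 simulated trials per setting. The interim conditions are assumed; the documents state no rule for starting Stage 2.

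| Condition on the interim | Pooled A v B | New A v Stage 1 B |
|---|---|---|
| none | 5.0% | 5.0% |
| difference favoured A | 10% | 9% |
| one-sided p < 0.05 | 54% | 26–27% |

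Against 15 fresh controls, new A rejects 5.0% of the time under each condition. The excess therefore comes from reuse.

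**4. From conditional to overall.** Multiply each rate by the chance of meeting its condition under the null:
- interim favours A: 0.5 × 10.0% = 5.0% pooled; 0.5 × 8.9% = 4.5% new A only;
- interim p < 0.05: 0.05 × 54% = 2.7% pooled; 0.05 × 26% = 1.3% new A only.

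For one signature fixed in advance, the chance of both passing such a condition and rejecting does not exceed about 5%.

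**5. Effect of a period shift.** The shift is assumed, with no selection on the interim, and the other settings are as in step 3.
- 0.25 SD in the new patients, favouring A: about 12% pooled, 18% new A only.
- 0.25 SD the other way: about 1.7 to 1.8% pooled, 0.9% new A only.

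Pooling carries more reuse bias; the new-A-only comparison is more exposed to drift.

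**6. Precision.** The 95% CI half-width is t₀.₉₇₅ × s × √(1/n₁ + 1/n₂), with s pooled from the quoted SDs (0.66 and 0.64).
- 35 v 15: 2.011 × 0.654 × 0.309 = 0.41.
- 20 v 15: 2.035 × 0.652 × 0.342 = 0.45.
- 35 v 8: 2.020 × 0.657 × 0.392 = 0.52.
- 20 v 8: 2.056 × 0.655 × 0.418 = 0.56.

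The planned difference is 0.37 − (−0.30) = 0.67.

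**The case against.** The strongest reply is that the plan does not claim much. It calls itself a pilot. Section 12.2.6 allows p-values in efficacy analyses to be nominal. Section 12.1.1 discusses primary endpoints under efficacy, and 12.2.5.1 applies its analysis sets to primary endpoints. On that reading the full analysis set (all dosed patients) already settles that Group A is pooled, and the intention-to-treat set (all randomised patients) supplies a randomised-only sensitivity analysis. Section 8.4 places the RNA sequencing at one core facility, which limits some sources of drift.

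Much of this is fair, and it argues for a wording and reporting change, not a redesign. It does not remove the point. Section 1.2 frames Stage 2 as a test against a null hypothesis, and 12.2.3 gives it an alpha and a power. Nominal status does not make the control concurrent. A randomised-only analysis would consist of Stage 1 data, the source of the hypothesis. One facility does not exclude differences between batches or patient populations over time.

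Two stronger readings are tempting. One is that the true type I error is 54%. Steps 3 and 4 show why that does not follow: the figure is conditional on an assumed interim result. Choosing this signature from many could inflate the overall rate, but the documents do not describe that choice and it was not simulated. The other is that every Group B patient helped to generate the hypothesis. Section 1.1 gives 35 enrolled patients and does not say how many had expression data, so this holds for the group but is not shown patient by patient.

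**Conclusion.** The point holds as a mislabelled control and an over-strong implied claim. The contradiction between sections 1.2 and 12.2.3 and the enrolment text rests on the documents alone. So does the derivation of the hypothesis from interim data. That Stage 1 Group A is also reused is an inference from the power statement; Group B is reused either way.

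The conditional rates rest on assumed interim results and Stage 1 sizes, and the shift figures on assumed drift. Conditioning on a favourable interim raises the rejection rate, whereas drift can act in either direction. The documents do not support a statement that the design's overall error rate exceeds 5%. They do support saying that a significant Stage 2 result is hypothesis-derived and, for the new patients, non-randomised, so it cannot stand as independent confirmation at 5%. This should be corrected before the Stage 2 analysis.

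**What to change.** 1. In sections 1.2.2 and 12.2.3, replace the Stage 2 description of the control with: *Stage 1 Group B, non-concurrent and non-randomised for Stage 2 patients*.
2. In section 12.2.6.1, keep pooled Group A v Stage 1 Group B, as 12.2.3 implies, as the main analysis. Add new Stage 2 Group A v Stage 1 Group B. Give each difference a confidence interval. State that both reuse Stage 1 Group B, and say which is more affected by reuse and which by drift. Describe the result as hypothesis-derived and non-randomised for Stage 2 patients, and do not present it as a confirmatory 5% test.
3. As a related but separate point, section 12.2.6.3 does not limit the exploratory A v B log-rank tests for PFS and OS to randomised patients. Base them on Stage 1, and show Stage 2 Group A as a separate curve.

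The cost is one extra comparison and a more modest claim, with no added patients. The interval half-widths in step 6 stay below the planned difference of 0.67, though with little to spare if only 8 controls have data.
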